Perceived Intervention Value			final month
Global Impression of Change			final month

below. All statistical analyses will be performed using SAS® version 9 (SAS Institute, Inc., Cary, North Carolina) by the study statistician [name]. Participant flow will be summarized using a CONSORT diagram.⁹⁸ Data will be summarized by intervention arm and time point as well as baseline to follow-up change using appropriate descriptive statistics. First, the baseline participant characteristics will be compared between the two arms. Any significant differences will be noted and accounted for as covariates in the sensitivity analyses. Second, primary and secondary analyses to address the aims will be performed as outlined below using multiple imputation for missing data. The primary analysis will be performed to test the primary hypotheses H1.1 about the ODI. Secondary analyses will be performed for remaining hypotheses, secondary outcomes and other exploratory analyses. Third, we describe below our primary approach to missing data and a set of sensitivity analyses by including additional covariates, ignoring missing data, and reasonable alternative statistical modeling strategies to assess the robustness of our findings.

Baseline Comparison:

Due to the large sample size and the randomization scheme balanced with respect to site, it is highly unlikely that baseline participant characteristics will be significantly different between the arms. If we do find any, they will be included as covariates in the sensitivity analyses. We will not alter the primary analysis to preserve its a priori nature and predictability. We will use independent samples t- or Wilcoxon rank sum tests, as appropriate based on distributional properties, to compare continuous baseline characteristics between the intervention arms. For categorical baseline participant characteristics, we will use chi-square and Fisher's exact tests, as appropriate. Statistical significance of the intervention term will be interpreted as indicating the need to include them as covariates in sensitivity analyses.

Aim 1 Primary Analysis:

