We will fit a linear mixed model with baseline to follow-up change in ODI score as the dependent variable; intervention arm (ABC/UC), follow-up time point (6/12 months) and their interaction as fixed effect of main interest; baseline ODI as a fixed effect covariate; and a participant random effect to account for multiple repeated assessments of the same participant over time. The statistical significance at $\alpha=0.05$ of the ABC vs UC means contrast at the 6-month point will serve as the formal test of the primary hypothesis H1.1. Upon confirming the H1.1 primary hypothesis, we will compute the number-needed-to-treat (NNT) as the reciprocal of the between-intervention difference in percentages of those showing a meaningful ODI improvement above its MCID.

Aim 1 Secondary Analyses:

To characterize the intervention actually received under ABC care, we will describe the conditions identified, further evaluations/initiated treatments and their responses recorded in the form that tracks response to treatment and additional management plans (see Appendix 12). We will employ the same analytic strategy described above for ODI (under primary analysis) for our secondary continuous outcomes pain severity, quality of life and falls efficacy. The statistical significance of the ABC vs UC means contrast at the 6- and 12-month points will serve as the formal tests of the secondary hypotheses H1.2.

Measures of healthcare utilization between 6 and 12 months in H1.3 (prescriptions/refills of opioids and inappropriate medications for elderly, invasive procedures, emergency room/hospital visits) are mostly in the form of counts. As such, we will fit a series of generalized linear models with each count utilization outcome as the dependent variable, a negative binomial distribution to account for any over dispersion and a logarithmic link function for the count outcome, actual person-time of exposure with opportunity for reporting utilization outcome as an offset, and intervention arm (ABC/UC) as the independent factor of interest. Intervention arm incident rate ratios and their statistical significances will constitute tests of H1.3.

Aim 2 Analyses:

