The goal is to explore whether ABC vs UC differences in improvement vary across participant subgroups of interest (effect modification). We will add each of the subgroups (based on baseline CLBP-associated disability, anxiety/ depression, mild cognitive impairment and obesity) and associated subgroup \times intervention group interaction effects as additional fixed effects in the above statistical models. Rigorous methodological guidelines for subgroup analyses require significant interaction effects for making conclusions of differential intervention effects in subgroups.⁹⁹ As such, we will first construct difference-in-difference type means contrasts representing the difference in ABC vs UC effects in different subgroups at each of the follow-up time points. If and only if the said interaction contrast is significant, we will estimate ABC vs UC differences and

their statistical significance within those subgroups.

Missing Data:

The best approach for handling missing data is to prevent it. We will use the methods described earlier to retain participants and prevent missing data. Despite our best efforts, missing data will occur. We will clearly document those with missing data and reasons in the CONSORT diagram, and compare those with missing data to complete data with respect to available data. Statistical guidelines for handling missing data recommend methods such as multiple imputation, which considers the uncertainty involved in imputing missing data.¹⁰⁰ Multiple imputation is arguably the best available objective method to analytically account for missing data under the ignorable or missing-at-random (MAR) assumption. Specifically, we will generate M=5 imputed values for each missing value, analyze the 5 datasets as though complete, and finally combine the results appropriately so that they reflect the uncertainty involved in imputation. SAS® MI and MIANALYZE procedures will be used. Other approaches to missing data, including the naïve approaches of ignoring the missing values and last-value-carried-forward (LVCF) will also be considered in sensitivity analyses and robustness of the results to using these approaches will be examined.

Sensitivity Analyses:

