We will perform a series of sensitivity analyses to ensure the robustness of our results against various assumptions. One such analysis will involve inclusions of baseline participant characteristics significantly different between groups as additional covariates in the linear mixed and generalized linear models above. Another will involve sensitivity of results to missing data handling techniques. In addition, if analyses of residuals from the models show violations of statistical assumptions, we will consider fitting models after Box-Cox transforming¹⁰¹ the continuous variables. Finally, a reasonable alternative to the proposed negative binomial models for count data representing healthcare utilization measures is the zero-inflated Poisson model.¹⁰² We will examine the sensitivity of our findings for utilization outcomes against this alternative modeling strategy.

Sample Size Justification and Statistical Power:

Planned sample size is 310 participants. Prior data and assumptions include a between-subject standard deviation of 18 points for pre- to post-intervention change in the primary outcome ODI¹⁰³; a conservative estimate of a minimally clinically important difference (MCID) of 7 points¹⁰⁴; a conservative dropout rate of 15% from other back pain trials¹⁰⁵; using published methods implemented in commercial software (PASS 2012®, Number Cruncher Statistical Systems, Kaysville, Utah), with 310 patients and 280 anticipated completers, we will be able to detect an observed primary outcome difference as small as 7 points with 90% power in a 2-tailed test at the $\alpha=0.05$ level.

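### Five imputations with no stated seed leave a borderline primary result dependent on the random draw, and no controlled departure from missing-at-random is pre-specified

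*Combined protocol and SAP*

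**What the plan says.** The Overview in section 5.6 makes imputation part of the main analysis: "primary and secondary analyses to address the aims will be performed as outlined below using multiple imputation for missing data". The Missing Data paragraph justifies it as a method to "analytically account for missing data under the ignorable or missing-at-random (MAR) assumption", and sets the number: "Specifically, we will generate M=5 imputed values for each missing value, analyze the 5 datasets as though complete". On software it adds "SAS® MI and MIANALYZE procedures will be used". It states no seed, no imputation model, no auxiliary variables and no check on Monte Carlo error.

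The test that depends on this is in Aim 1 Primary Analysis: "The statistical significance at $\alpha=0.05$ of the ABC vs UC means contrast at the 6-month point" is the formal test of H1.1, and the number needed to treat is computed only if H1.1 is confirmed.

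For sensitivity, the same paragraph says "Other approaches to missing data, including the naïve approaches of ignoring the missing values and last-value-carried-forward (LVCF) will also be considered in sensitivity analyses". The Sensitivity Analyses paragraph refers again to missing-data techniques but names no others. The plan will also record reasons for missing data and compare participants with and without it. Section 5.7 ends follow-up calls, and so data collection, when a participant withdraws.

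**The concern.** Two separate weaknesses meet in one paragraph.

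The first is Monte Carlo error. Multiple imputation draws random values, so the pooled estimate, its variance and its degrees of freedom all change with the seed. With five draws this noise is not negligible against a fixed 0.05 line. Because no seed is pre-stated, nothing in the plan determines which of the possible p-values is the official one. That sits badly with the plan's stated wish to keep the primary analysis a priori and predictable.

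The second is that the robustness checks do not probe the assumption most open to doubt. Participants know which kind of care they receive, and withdrawal ends data collection, so no later outcomes exist to show whether those who left did worse than predicted. If imputation, the analysis ignoring missing values and last value carried forward all agreed, the report could claim robustness without having varied the outcome of missing ABC participants in any controlled way.

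**Working it through.** **Inputs.** From section 5.6: M = 5; two-sided alpha 0.05; SD of ODI change 18; design difference 7 points; dropout 15%; 310 randomised; 280 anticipated completers. Allocation is 1:1 (section 5.5). Assumed, because the documents do not give it: fraction of missing information (FMI) 0.15, with a range of 0.05 to 0.25. An FMI near the dropout rate is what one expects if other data add little.

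**The plan's own figure.** With 140 per arm, SE = 18 × sqrt(4/280) = 2.15, 7/2.15 = 3.25, and power is 90.2% (90.0% with the t distribution). The stated 90% reproduces. At 15% dropout, 310 × 0.85 = 263.5 remain, SE = 18 × sqrt(4/263.5) = 2.22, and power is 88.4%. The SE of 2.22 is used below.

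**Size of the seed effect.** With the observed data fixed, the Monte Carlo SD of the pooled estimate is sqrt(FMI/M) standard errors:
- M = 5: sqrt(0.15/5) = 0.17 SE, or about 0.38 ODI points
- M = 50: sqrt(0.15/50) = 0.055 SE, or about 0.12 points

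This formula alone understates the spread of p-values, because the between-imputation variance is also estimated from only M draws. The next figures therefore simulate Rubin's rules in full, with Barnard-Rubin degrees of freedom. The unlimited-imputation result is set at z = 2.1 (p = 0.036).

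| FMI | M | Share of seeds with p > 0.05 |
|---|---|---|
| 0.05 | 5 | about 14% |
| 0.15 | 5 | about 34% |
| 0.25 | 5 | about 43% |
| 0.15 | 50 | about 2% |
| 0.15 | 100 | about 0.2% |

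At FMI 0.15 and M = 5, 90% of seeds give p between about 0.017 and 0.090. Setting p = 0.036 on the t rather than the normal scale changes 34% to 32%.

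**How often it would matter.** At FMI 0.15, averaged over simulated trials with a true 7-point effect, two seeds disagree about p < 0.05 in 5.4% of trials at M = 5 and 1.0% at M = 100. With a true 4.5-point effect the figures are 10.0% and 2.0%. Away from the line the problem fades: at an unlimited-imputation p of 0.01, 98.7% of five-imputation seeds are significant. At an observed 7-point difference (z about 3.16), about 0.01% of seeds exceed 0.05.

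**Departure from missing-at-random.** Suppose each missing ABC participant did d points worse than imputed. With 15% of the arm missing, the estimated benefit falls by 0.15d. Holding the SE at 2.22, significance needs 1.96 × 2.218 = 4.35 points.
- 5-point estimate: d = (5 − 4.35)/0.15 = about 4.4 points
- 7-point estimate: d = (7 − 4.35)/0.15 = about 17.7 points

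If instead 280 complete (9.7% missing, SE 2.15, threshold 4.22), the shifts are (5 − 4.22)/0.097 = about 8.1 and (7 − 4.22)/0.097 = about 28.7.

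**Reference-based case.** If the missing ABC participants had usual-care outcomes, a 5-point estimate becomes 0.85 × 5 = 4.25. With the SE held at 2.22, z = 1.92 and p moves from 0.024 to 0.055. If the SE shrinks in proportion, to 0.85 × 2.22 = 1.89, z and p = 0.024 do not change. The variance method decides the answer, so it must be stated in advance.

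**The case against.** The strongest defence is that five imputations are legitimate. Rubin's rules allow for the small number: simulated type I error stays at about 4.9%, relative efficiency is about 0.97, and the power cost is about 1.5 points (86.8% against 88.3% at M = 100). At the design effect most trials would reach the same verdict under any seed. ODI is also collected at baseline and every three months, so a good imputation model could bring the FMI below 0.15. All of this stands, and it confines the first half of the point to borderline results.

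Four stronger readings are tempting, and the documents do not support them.
- A reader might infer that the plan tests no departure from missing-at-random. Last value carried forward is such a departure: it fixes no change after the last value. It is crude and uncontrolled, but it is not nothing. The list of alternatives is also open-ended.
- A reader might take ignoring the missing values to mean a complete-case analysis resting on a stronger assumption than missing-at-random. In the planned mixed model it is an available-case likelihood analysis, itself valid under missing-at-random. The fair criticism is that it largely repeats the main assumption.
- A reader might infer biased outcome assessment from the open treatment. Section 5.5 has follow-up collected by coordinators masked to arm. What remains is that participants know their care and may leave because of it.
- A reader might infer that differential ABC dropout is expected. Nothing in the documents shows this; it is a possibility that the plan should be able to examine.

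**Conclusion.** The point holds in two limited parts. First, five imputations with no stated seed give a valid but imprecise primary test. If unlimited imputations would give p = 0.036, about one seed in three reverses the verdict at an assumed FMI of 0.15 (14% to 43% over FMI 0.05 to 0.25). The effect is small for results well away from 0.05. Second, the plan pre-specifies no analysis that varies the outcomes of missing participants in a controlled way. Agreement among its three approaches would therefore say little about robustness to missing ABC participants doing worse than predicted. On the plan's SD and dropout, with the SE held fixed, a 5-point result would be fragile (a shift of about 4.4 points, below the plan's 7-point minimal clinically important difference) and a 7-point result sturdy (about 17.7). These sizes rest on the assumed FMI, equal arms and a fixed SE. The change should be made, because it costs very little; it does not cast doubt on the design.

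**What to change.** In the Missing Data paragraph:
- Raise M to about 100, and at least 50. State the seed and the imputation model, including any auxiliary variables, before outcomes are seen by arm.
- Add a delta-adjusted analysis that shifts imputed 6-month ODI change separately by arm, and report the tipping point. Extend the range until the conclusion changes; a cap of 10 points would miss the tipping point for a 7-point estimate.
- Add a reference-based analysis in which missing ABC outcomes are imputed from usual care, with its variance method named.
- Place these beside last value carried forward or in its place, and describe the analysis ignoring missing values as a check under the same assumption rather than a test of it.

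The plan names only SAS version 9, so confirm that the release in use supports the chosen method; a simple shift can be added to the imputed values in any release. The cost is computing time, some added text and a few table rows. Sample size, visits and data collection do not change.

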To ascertain the feasibility of the revised (no imaging required) recruitment strategy, we reviewed 100 randomly selected charts at each site from among the total available pool (i.e., those available for pre-screening). As shown in Table 3, data pulled from our 3 participating sites over the past 12 months revealed 17,235 Veterans age 65-89 with a diagnosis of low back pain and who had seen their PCP within the prior 6 months (7,486 from Los Angeles, 4,739 from Pittsburgh and 5,010 from Richmond). Pre-screening excluded 40% at Los Angeles, 50% at Richmond, and 39% at VAPHS. The most common reason for ineligibility across sites was prior spine surgery (60% of those excluded at Los Angeles, 34% of those excluded at Richmond, and 38% of those excluded at VAPHS). Total numbers available for on-site assessment following telephone screening and those eligible following on-site assessment were calculated based on Pilot Study #2 (Figure 2) and the results are shown in Table 3. Thus, we expect to easily meet our recruitment goals of 55 participants per site per year.

Perceived Value of ABC Care. Pilot Study #2 is ongoing

[figure not shown]

Figure 2. Status of Pilot Study #2

Table 3. Annual Recruitment: Potential Enrollees

Number of Veterans...	VAPHS	Los Angeles	Richmond
Available for pre-screening	4,739	7,486	5,010
Eligible for telephone screening	2,890	4,491	2,505
Eligible for on-site assessment	1,600	2,470	1,387
Eligible after on-site assessment	1,194	1,828	1,035

Table 4. Value of ABC Care: Veteran Quotes

- I am sleeping better, having less pain, and able to do things I couldn't do before, like cut the grass.
- My pain is tolerable now.
- Before the study I was getting one hour of sleep; now I am doing much better.
- I can stand longer and the pain is not as intense. Before the study I could only walk 20 yards and my back felt like it was on fire. I no longer feel that.
- I wouldn't trade [being in the study] for a million dollars. I am fortunate to be a veteran and to be able to get this kind of care. I'm sincere about it.

thus we have not broken the study blind. As per our study protocol, an unmasked research coordinator has conducted exit interviews at study completion (6 months follow up) for participants that were randomized to PCC care. Noteworthy feedback is in Table 4.

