About 450 Veterans (150 from each site), age 65-89 with chronic low back pain (CLBP) will be recruited, (to target randomizing 310 participants), from the VA Pittsburgh Healthcare System (VAPHS), the VA Greater Los Angeles Healthcare System (Los Angeles, CA), and the Hunter Holmes McGuire VA Medical Center (Richmond VA). We anticipate the need to telephone screen ~1050 (i.e., ~175 per site per year) to obtain 450 participants who meet all inclusion and exclusion criteria. No one will be excluded on the basis of race, gender or ethnicity. Based upon the data from each of the three sites, we anticipate that our overall participant sample will be 97% male, 3% female, 2% Hispanic or Latino, 98% Not Hispanic or Latino, 1% American Indian/Alaskan Native, 0% Asian, 2% Native Hawaiian or Pacific Islander, 18% Black or African American, and 79% White or Caucasian. Non-Veterans will not be recruited to participate. Vulnerable subjects will not be enrolled, including children and prisoners. Neither pregnant subjects nor women of childbearing potential will be included because we are targeting older adults with chronic LBP.

Costs and Payment:

In order to compensate participants for their time, they will be paid \$100 in total, with payments spaced out over 12 months. They will be paid \$40 for their baseline visit and \$30 for their final follow-up visit. An additional \$30 will be paid after their 6-month follow-up call.

Participants will be paid by check or electronic bank deposit, \$100 in total, with payments spaced out over up to 12 months. They will be paid \$40 for their baseline visit and \$30 for their final follow-up visit. An additional \$30 will be paid after their 6-month follow-up call. Participants may drop out of the study at any time without forfeiting the payments they have already received. Payments typically take between 10 days and two weeks to reach Veterans.

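### The sample-size statement assumes 15% dropout from 310 randomized but counts 280 completers, a 9.7% loss; at 15% there are about 263 and unadjusted power is about 88%, not 90%

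*Combined protocol and SAP*

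**What the plan says.** The sample-size paragraph of section 5.6 (Sample Size Justification and Statistical Power) gives all the inputs together:

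- Size: "Planned sample size is 310 participants". Section 5.1 (Participants) confirms that this is the number randomized: "to target randomizing 310 participants".
- Variability: "a between-subject standard deviation of 18 points for pre- to post-intervention change in the primary outcome ODI".
- Target difference: "a conservative estimate of a minimally clinically important difference (MCID) of 7 points".
- Attrition: "a conservative dropout rate of 15% from other back pain trials".
- Result: "with 310 patients and 280 anticipated completers, we will be able to detect an observed primary outcome difference as small as 7 points". The stated power is 90%, for a two-sided test at alpha 0.05.

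The paragraph does not show how 280 was obtained from 310, and it does not say whether the 15% applies at 6 or at 12 months. The primary test (section 5.6, Aim 1 Primary Analysis) is the 6-month contrast between arms in a linear mixed model for change in ODI. The model has baseline ODI as a covariate, and missing values are to be multiply imputed.

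**The concern.** The attrition assumption and the completer count sit in the same sentence and contradict each other. The power figure is calculated on the completer count. If the 15% is what the team expects, the power quoted for the primary hypothesis belongs to a larger analysed sample than 310 randomized would supply. There is no slack to absorb the gap, because 280 is the smallest equal-arm total that reaches 90% in the exact t calculation.

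The wording adds a smaller problem. Power is the chance of a significant result when the true difference has a given value; it does not describe the observed difference. Since 7 points is also the plan's minimal clinically important difference, a reader could take the sentence to mean that a significant result implies an observed benefit of at least 7 points. It does not.

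**Working it through.** **Inputs.** All are from the sample-size paragraph of section 5.6 except the allocation, which is in section 5.5 (Randomization and Blinding): 310 randomized 1:1; dropout 15%; completers 280; SD of change 18; difference 7; two-sided alpha 0.05.

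**Step 1: reproduce the plan's 90%.** With 140 per arm:

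- SE = 18 × √(1/140 + 1/140) = 2.151
- 7 / 2.151 = 3.254
- Normal approximation: Φ(3.254 − 1.960) = 90.2%
- Exact noncentral t: 90.0%

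The plan's figure reproduces. The exact t calculation needs 140 per arm for 90% power (139 per arm gives 89.8%).

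**Step 2: check the completer count.**

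- 310 × (1 − 0.15) = 263.5, that is 263 or 264
- 1 − 280/310 = 9.7%
- Gap: 280 − 263.5 = 16.5 completers, or 16.5/280 = 5.9%

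The usual ways of allowing for dropout do not link the three numbers either. Dividing, 280/0.85 = 329.4, or about 330 randomized. Multiplying, 280 × 1.15 = 322. Neither gives 310.

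**Step 3: power at the plan's own dropout rate.** With 132 and 131 per arm:

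- SE = 18 × √(1/132 + 1/131) = 2.220
- 7 / 2.220 = 3.153
- Normal approximation: Φ(3.153 − 1.960) = 88.4%
- Exact noncentral t: 88.1%

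| Completers | Power for 7 points, normal | Power for 7 points, exact t | Difference detectable with 90% power (exact t) |
|---|---|---|---|
| 280 | 90.2% | 90.0% | 7.0 |
| 264 | 88.5% | 88.3% | 7.2 |
| 263 | 88.4% | 88.1% | 7.2 |

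**Step 4: true versus observed.** The smallest observed difference that reaches two-sided significance is the t critical value times the SE: about 4.2 points with 280 completers and about 4.4 with 263. A significant result can therefore fall well below 7.

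**Step 5: what baseline adjustment could recover.** The document gives no correlation between baseline ODI and change in ODI, so this step rests on an assumption. With correlation r, the residual SD is 18 × √(1 − r²). At 263 completers (exact t):

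| Assumed r | Power for 7 points |
|---|---|
| 0 | 88.1% |
| 0.2 | 89.4% |
| 0.25 | 90.1% |
| 0.3 | 90.9% |
| 0.5 | 95.2% |

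**The case against.** The best defence is that the contradiction makes little practical difference. The stated 90% is right for the stated 280 completers. Moving to 263 costs about two percentage points of power and 0.2 of an ODI point, less than ordinary uncertainty in the SD would cost: at 280 completers an SD of 19 instead of 18 already gives 86.7%. The 88% also describes an unadjusted comparison of completers, which is not the planned analysis, and a baseline correlation of about 0.25 would restore 90%. If the 15% is a 12-month figure, fewer than 15% may be lost by month 6, when the primary contrast is tested; section 5.7 keeps data collected before withdrawal.

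All of this stands as a limit on the size of the problem. It does not remove the contradiction. The sample-size paragraph claims no gain from the covariate or from imputation, gives no correlation, and attaches no time point to the 15%. It bases power on completers, and those do not match its attrition rate.

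Three stronger readings are tempting, and the document does not support them:

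- **The trial fails to deliver its power.** A reader might infer this from 263 against 280. The shortfall is about two points on a simplified calculation, and the planned model may recover it.
- **The 280 is left over from a 330-participant design.** The arithmetic invites this. Section 2.0 speaks of "recruitment goals of 55 participants per site per year"; section 5.1 plans about 1050 telephone screens at about 175 per site per year, and 1050/(175 × 3) = 2 years; 55 × 3 × 2 = 330, and 330 × 0.85 = 280.5. But no such design is recorded, and section 2.0 does not say that its figure counts randomized participants. It is one possible explanation and nothing rests on it.
- **The word 'observed' alters the success criterion.** It does not. The Aim 1 Primary Analysis defines success as significance at 0.05 and requires no observed difference of 7.

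**Conclusion.** Wrong as written, and minor. The figures of 310 randomized, 15% dropout and 280 completers cannot all hold. At 15% the completer count is overstated by 16 or 17. On the plan's unadjusted inputs, power for a true 7-point difference is then about 88% and not 90%, and the difference detectable with 90% power is about 7.2 points.

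The inconsistency is plain arithmetic and needs no assumption. The 88% assumes an SD of 18, equal allocation, a 15% loss in force at the 6-month assessment, and no gain from the baseline covariate or from imputation. If the loss by 6 months is smaller, or if baseline ODI predicts change, power is higher. The test, the alpha and the randomization target are unaffected.

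**What to change.** Restate the sentence in section 5.6 in one of two ways.

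1. If 15% is the intended assumption: *With 310 randomized and 15% dropout (about 263 completers), power is about 88% for a true 7-point difference (90% for about 7.2 points), before any gain from baseline-ODI adjustment.*
2. If 280 is the intended count: give the loss of about 10% at 6 months that yields it, with its justification, and drop the 15% or explain that it refers to a different time point.

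In either case, replace 'observed' with 'true' and state the time point of the dropout rate. If the sponsor wants to rely on the covariate to reach 90%, the assumed correlation and its source should be given.

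The cost is one sentence. Under the first option the stated power becomes slightly less favourable. No extra patients are needed, and no procedure or analysis changes.
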